# 5.5. Exploratory Endpoints

## 5.5.1. Definitions

# 5.5.1.1. Binary Endpoints

## 5.5.1.1.1. Sustained HBsAg Response

The definitions of sustained response are as follows (yes/no):

Definition 1:

- For participants with follow-up week 48 data: Participants who have a > 1 log decline in HBsAg at follow-up week 48 and have an HBsAg <1000 IU/mL at follow-up week 48.
- For participants without follow-up week 48 data: HBsAg values have a > 2 log decline at follow-up week 24 or >1.5 log decline at follow-up week 40 (most recent value used) compared to baseline and have an HBsAg <1000 IU/mL at the last available timepoint.

Definition 2: For participants with a >1 log decline in HBsAg from baseline at last follow-up visit: Among the most recent three visits, the difference between log HBsAg at 2 of 3 last visit and 1 of 3 last visit is <0.2, and the difference between log HBsAg at 3 of 3 last visit and 1 of 3 last visit is <0.2.

Definition 3: For participants with a >1 log decline in HBsAg from baseline at last follow-up visit: Among the most recent three visits, the difference between log HBsAg at 2 of 3 last visit and 1 of 3 last visit is <0.2, and the difference between log HBsAg at 3 of 3 last visit and 1 of 3 last visit is <0.2 and have an HBsAg <1000 IU/mL at the last available timepoint.

Due to the exploratory objectives of this Phase 2 study, additional sustained HBsAg response definitions may be explored according to the clinical interest.

# 5.5.1.1.2. Liver Stiffness Measurement

The following liver stiffness measurements (LSM) changes from baseline (in terms of reductions) will be evaluated over time at Week 24, FU Week 24 and FU Week 48:

- $\geq 2 \text{ kPa}$
- $\geq 4 \text{ kPa}$

# • $\geq 6 \text{ kPa}$

Only participants from sites with available VCTE (Fibroscan) will be included in the analysis. Within these participants, missing LSM (in kPa) at a specific timepoint will be considered as non-responders for that timepoint.

# 5.5.1.1.3. HBV RNA Cut-offs

The cut-offs for HBV RNA are as follows (yes vs no):

- TND
- <LOD
- < LLOQ
- <1000 copies/mL

The cut-offs for HBV RNA change from baseline are as follows (yes vs no):

- decrease by  $\geq 1.0 \log \text{ copies/mL}$
- decrease by  $\geq 2.0 \log \text{ copies/mL}$
- decrease by  $\geq 3.0 \log \text{ copies/mL}$

# 5.5.1.1.4. HBcrAg Cut-offs

The cut-offs for HBcrAg are as follows (yes vs no):

- < 3.0 log U/mL
- < 4.0 log U/mL

The cut-offs for HBcrAg change from baseline are as follows (yes vs no):

- decrease by  $\geq 1.0 \log U/mL$
- decrease by  $\geq 2.0 \log U/mL$
- decrease by  $\geq 3.0 \log U/mL$
- decrease by  $\geq$  4.0 log U/mL

# 5.5.1.2. Continuous Endpoints

# 5.5.1.2.1. Liver Stiffness Measurement

Severity of liver disease at the end of study intervention and follow-up versus baseline will be evaluated by the changes in fibrosis over time according to Fibroscan LSM.

Change from baseline is defined as the value at a given time point minus baseline value.

# 5.5.1.2.2. HBV RNA and HBcrAg

Actual values, changes from baseline (log transformed value) over time in HBV RNA and HBcrAg will be evaluated.
Change from baseline is defined as the value at a given time point minus baseline value.

## 5.5.2. Analysis Methods

Summaries and graphs will be provided for each intervention arm and analysis phase, unless specified otherwise.

Statistical comparisons of all exploratory endpoints among intervention arms will be done with no adjustment for multiplicity.

All exploratory endpoints will be analyzed based on the observed case data.

Inferential and descriptive subgroup analyses may not be performed if there are not enough data to perform the analyses.

### 5.5.2.1. Binary Endpoints

The count and proportion (%) of participants achieving the endpoints defined in Section 5.4.2.1 will be summarized. The associated 90% CI may also be included.

### 5.5.2.2. Continuous Endpoints

The methods of analysis of the continuous exploratory endpoints will be the same as those described in Section 5.4.2.2.

Waterfall plots for changes from baseline HBcrAg and fibrosis will also be presented.

Subsections below describe the additional analyses planned for only those specific exploratory endpoints that require further evaluations.

#### 5.5.2.2.1. Liver Stiffness Measurement

The changes from baseline at Week 24, FU Week 24, and FU Week 48 will be summarized using descriptive statistics (n, mean, SD, SE, 90% CI, median, minimum, maximum) by intervention arm. The comparison among intervention arms will be done using ANCOVA with intervention arm, randomization stratification factor as main effects and baseline score as covariate.

At each assessment time point, a frequency distribution of severity scores will be produced.

## 5.5.2.2.2. Anti-HBs Antibodies

For all participants with positive anti-HBs antibodies at baseline who will reach HBsAg seroclearance (as defined in Section 5.4.1.1.2), descriptive statistics will be calculated for the change of anti-HBs antibodies level from baseline at the timepoint and subsequent timepoints when achieving the HBsAg seroclearance. In an additional summary, the change of anti-HBs antibodies level from baseline at the specific timepoint and subsequent timepoints will be summarized descriptively for the subset of the participants achieving HBsAg seroclearance at any time before or at that given timepoint.

#### 5.6. Safety Analyses

Summaries will be provided on the overall population and by intervention arm and analysis phase unless specified otherwise.

Safety and tolerability will be assessed by evaluating treatment emergent-adverse events (TEAEs), immune related AEs, physical examinations, vital signs measurements, clinical laboratory tests (including hematology, blood biochemistry, blood coagulation, and urinalysis), renal biomarkers and ECGs.

For all continuous safety variables, descriptive statistics by intervention group will include the N, mean, standard deviation, standard error, median, minimum, and maximum. Categorical variables will be summarized by intervention group using frequency counts and percentages.

### 5.6.1. Extent of Exposure

The number and percentage of participants who receive each study agent within a study intervention will be summarized.

Descriptive statistics for duration of each study agent within a study intervention (N, mean, SD, SE, median, and range (minimum, maximum)) during the study intervention period will be summarized.

Because of the different route and frequency of treatment administration across the 3 agents (for JNJ-3989 one subcutaneous injection every week for the first 4 weeks and then once every 4 weeks, for nivolumab one intravenous infusion at Week 16 in Arm 1 and Week 16, 20 and 24 in Arm 2, and for NA once daily tablet) the total duration for each study agent as follows:

- JNJ-3989:
  - Discontinuation of JNJ-3989 before Week 4:
    - [Min ((Date of last JNJ-3989 (loading dose) injection +6 days), Date of trial disposition, cut-off date) Date of first JNJ-3989 injection+1] / 7
    - Otherwise: [Min ((Date of last JNJ-3989 injection + 27 days), Date of trial disposition, cut-off date) Date of first JNJ-3989 injection + 1] / 7
- Nivolumab: [Min (Date of the last nivolumab infusion + 27 days, Date of trial disposition, cut-off date) Date of first nivolumab infusion + 1] /7

Cutoff dates will be defined to match the prespecified timepoints for interim analyses and the primary analysis, respectively (Section 5.8).

The number and percentage of participants who skipped any dose of JNJ-3989 or nivolumab will be summarized separately for each study intervention by intervention arm during the study intervention period. Additionally, the number and percentage of participants who missed 2 or more JNJ-3989 injections, or who missed 1 or more nivolumab infusion will be presented.

Study intervention compliance will be summarized descriptively. See Appendix 7 Intervention Compliance for further details.

#### 5.6.2. Adverse Events

The verbatim terms used in the CRF by investigators to identify adverse events will be coded using the Medical Dictionary for Regulatory Activities (MedDRA version 25.0). Any AE occurring at or after the initial administration of study intervention is considered to be treatment emergent. If the event occurs on the day of the initial administration of study intervention, and either event time or time of administration are missing, then the event will be assumed to be treatment emergent. If the event date is recorded as partial or completely missing, then the event will be considered to be treatment emergent unless it is known to be prior to the first administration of study intervention based on partial onset date or resolution date. All reported treatment-emergent adverse events will be included in the analysis. For each adverse event, the number and percentage of participants who experience at least 1 occurrence of the given event will be summarized by intervention arm.

Summary tables will be provided for treatment-emergent adverse events:

- AEs
- Serious AEs (SAEs)
- AEs leading to discontinuation of any study agent within a study intervention
- AEs by relationship to each study agent within a study intervention
- AEs leading to dose interruption/dose modification of each study agent within a study intervention.
- AEs leading to systemic corticosteroid administration.

In addition to the summary tables, listings will be provided for participants who:

- Had SAEs
- Had AEs leading to discontinuation of each study agent within a study intervention

For participants reporting rash, a listing with specific grade will be provided.

Incidence of treatment-emergent adverse events of special interest will be summarized by analysis phase and overall

The adverse events of special interest include:

- Immune related AEs
- ALT/AST elevations
- Injection Site Reactions Related to JNJ-3989
- Infusion Reactions Related to nivolumab
- Renal Complications
- Hematologic Abnormalities (platelet count, hemoglobin, reticulocytes, neutrophil count)

The list of all preferred terms belonging to ALT/AST elevation, renal complications, and hematologic abnormalities is provided in Table 10 Appendix 8. Injection and infusion site reactions will be identified using the eCRF Injection Site Reaction Assessment form for JNJ-3989 and Infusion-related reactions for Nivolumab. Immune related AEs will be also identified using the eCRF Adverse events/Serious AEs form based on the related question.

A listing of participants who died will be provided.

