#### **2.3.2. Risks for Study Participation**

##### **2.3.2.1. Known Risks**

In the AROHBV1001 study, ISRs were the most frequently observed AEs assessed by the investigator as related to JNJ-3989 administered subcutaneously.

Immune checkpoint inhibitors (ICIs), such as anti-PD-1 monoclonal antibodies, target proteins that enhance the response of the immune system to tumor cells or HBV-infected hepatocytes. By stimulating the endogenous immune system however, there is the potential for adverse effects on other tissues by way of immune cell activation and inflammatory mechanisms. The potential immune-related AEs (irAEs) require close and more frequent monitoring, and early intervention such as administration of corticosteroids.

Safety risks for nivolumab are based on results from nonclinical toxicology studies and oncology clinical studies conducted with nivolumab, the known mechanism of action of nivolumab (ie, anti-PD-1 antibody), and the route of administration. irAEs and infusion-related reactions (IRRs) have been identified as important identified risks for nivolumab (ie, immune-related pneumonitis, immune-related colitis, immune-related hepatitis, immune-related nephritis and renal dysfunction, immune-related endocrinopathies, immune-related skin adverse reactions, other irAEs, and severe infusion reactions ([NSPC](#))).

The safety profile of nivolumab is manageable with the majority of AEs being Grade 1 or Grade 2 in severity based on the National Cancer Institute Common Terminology Criteria for Adverse Events (NCI-CTCAE). irAEs typically resolve after systemic treatment with corticosteroids or discontinuation of nivolumab treatment. Immune-related endocrinopathies such as hypothyroidism and adrenal insufficiency may require endocrine replacement therapy.

Treatment with anti-PD-1 medications is associated with a risk of HBV reactivation in CHB patients. This risk is reduced with concurrent NA treatment or continuation of ongoing NA treatment.

In a case series of cancer patients with HIV, HBV, or hepatitis C virus (HCV) infection treated with ICI therapy including chemotherapy plus immunotherapy, it was found that the safety and efficacy profile of ICI therapy is similar to that observed in those without chronic viral illness, suggesting that ICI therapy is a safe and effective treatment option for patients with HIV, HBV, or HCV infection suffering from advanced-stage cancer ([Shah 2019](#)).

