### **8.3.6. Guidelines for Management of Adverse Events of Special Interest Including Immune-Related Adverse Events**

Adverse events of interest are significant AEs that are judged to be of special interest because of clinical importance, known class effects or based on nonclinical signals. Immune-related AEs of interest that will be carefully monitored during the study include ALT/AST elevations including immune-related hepatic AEs, IRRs and other irAEs (including gastrointestinal AEs, neurological AEs, pulmonary AEs, renal AEs, endocrinopathies, rash, uveitis and visual complaints, lipase/amylase elevations, and infection). Other AEs of Special Interest related to JNJ-3989 that will be carefully monitored during the study include hematological abnormalities and ISRs.

AEs of Special Interest should be identified and reported to the sponsor's Medical Monitor and reported as an SAE if SAE criteria are met.

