### 8.3.6.3. Other Adverse Events of Special Interest Related to JNJ-3989

#### 8.3.6.3.1. Hematologic Abnormalities

Hematological abnormalities including Grade 3 and Grade 4 neutropenia, thrombocytopenia, anemia, and autoimmune hemolytic anemia were reported with nivolumab used in the oncology setting.

In the Phase 1/2a AROHBV1001 study with JNJ-3989, mild (Grade 1) transient thrombocytopenia was observed in 6 out of 84 participants receiving 3 SC injections of JNJ-3989 alone over a period of up to 12 weeks with background of NAs. The transient thrombocytopenia was not considered clinically significant. No thrombocytopenia or pancytopenia was observed in 12 participants when JNJ-3989 was given in combination with JNJ-6379 over a 12-week period in the same study.

Based on the nonclinical findings, any relevant abnormalities in hematologic parameters will be carefully monitored as described below:

- Platelet counts:  $<100,000$  cells/mm^3 (at least Grade 2 [DAIDS]) or  $<100$  GI/L or reduction from baseline by at least 50%.
- Hemoglobin: Decrease of at least 2 g/dL from baseline or at least Grade 2 (DAIDS).
- Neutrophil count: Treatment-emergent reduction to at least Grade 2 (DAIDS).

In case any of the above criteria are met, a confirmatory visit should be scheduled as soon as possible, preferably within 7 days of the receipt of the initial results. Confirmation of the results will trigger weekly or biweekly (every other week) unscheduled visits until improvement or stabilization of the respective parameter(s). Stabilization is defined as no further significant reduction over 2 consecutive visits.

In case of confirmed Grade 3 or Grade 4 hematologic abnormalities (platelet count, hemoglobin, and neutrophil count), discontinuation of JNJ-3989 (and nivolumab if applicable) should be considered. In case of discontinuation, NA treatment should be continued.

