Overall rationale of this SAP Amendment: The main reason for this SAP amendment was to align with the protocol amendment 2 that was performed due to difficult recruitment. Therefore, a strategic decision was taken to not extend further enrollment beyond the planned enrollment period and continue the study with a reduced sample size. In the meantime, there has been a new amendment (amendment 3 – 30 June 2023) of the protocol filed. The main reason for the protocol amendment 3 was the discontinuation of PD-1 inhibitor (nivolumab) as study intervention as of 20 June 2023 as an urgent safety measure (USM). Based on the observation of two cases of potential hyperthyroidism, the sponsor decided on 20 June 2023, to halt further nivolumab dosing effective immediately. Treatment with JNJ-3989 and/or nucleos(t)ide analog was continued as planned. The impact of this amendment 3 has been discussed and it has been agreed that this does not affect the Statistical Analysis Plan.

Section number and Name	Description of Change	Brief Rationale
1.2. Study Design	Reduction of	Due to difficult
	sample size.	recruitment.
3. Sample Size		
Determination		
5.1.9. Data Handling Rules	Revised ULOQ and Imputed Values	Improved for clarity
	data cutpoints for HBsAg, HBeAg	and precision.
	and HBcrAg.	
	Updated guidelines for the	
	imputation of HBV DNA.	
5.5.1.1.5. Anti-HBe	Analysis removed.	Qualitative anti-HBs
Antibodies		results are not
		collected.

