#### Table 5: Laboratory Parameters

Clinical laboratory tests will be displayed for the participants included in the safety analysis set.

Descriptive statistics and graphical displays will be presented for all chemistry, hematology, and urinalysis laboratory tests at scheduled time points.

Change from baseline over time will be summarized for chemistry, hematology, urinalysis tests and renal biomarkers and displayed.

Abnormality criteria (based on the criteria specified in the Modified DAIDS Toxicity Grade Scale (see Clinical Protocol Appendix 8, DAIDS Table with Modifications (DAIDS [Modified]))) will be applied to baseline and postbaseline values or in accordance with the normal ranges of the clinical laboratory if no gradings are available.

Postbaseline abnormalities will be compared with their corresponding baseline result:

• For toxicity grades, treatment emergent (TE) will be concluded if the postbaseline grade is worse than the baseline grade.

CONFIDENTIAL – FOIA Exemptions Apply in U.S.

- For abnormalities based on normal range and/or criteria: If the postbaseline value is above the upper limit and the baseline value is below the upper limit (e.g. Normal or Low), then the postbaseline abnormality will be considered TE. The same applies to the postbaseline value being below the lower limit with the baseline value being above the lower limit (e.g. Normal or High).
- If the baseline value is missing, a postbaseline abnormality will always be considered as TE.

For each lab parameter, a worst-case analysis will be performed by using the worst abnormality and/or worst toxicity grade lab value and time point per participant. The worst toxicity case is the value associated to the highest toxicity grade and is derived per parameter and toxicity direction (hypo/hyper). Worst-case will be derived withing each analysis phase, including unscheduled assessments. For abnormalities, in case the same participant has both abnormalities (low and high) for the same lab test within the same phase, the participant will be counted in the analysis for both toxicity directions (abnormally high and low).

In case continuous laboratory results are not numerically expressed, but as a character (e.g. 'less than 2', '>25'), these results will be numerically imputed as follows:

- If the analysis result contains '<' then the result will be multiplied by 0.999 (e.g. <6.1 becomes 6.0939).

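### The SAP's closed AESI term list has no hepatitis or haemolytic anaemia terms, no term list backs the immune-related category, and no AE table by severity grade is planned

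*SAP*

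**What the plan says.** Two secondary safety endpoints in SAP 1.1 are involved: the proportion of participants with AEs of interest, and a safety profile that includes how frequent and how severe AEs and immune-related AEs are.

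SAP 5.6.2 names six AESI groups: immune-related AEs, ALT/AST elevations, injection site reactions, infusion reactions, renal complications and hematologic abnormalities. For three of them, "The list of all preferred terms belonging to ALT/AST elevation, renal complications, and hematologic abnormalities is provided in Table 10 Appendix 8". Injection and infusion reactions come from their own eCRF sources. For the remaining group, "Immune related AEs will be also identified using the eCRF Adverse events/Serious AEs form based on the related question".

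The protocol's scope is wider. Section 8.3.6 puts ALT/AST elevations with immune-related hepatic AEs, infusion reactions, and gastrointestinal and neurological events among the immune-related AEs of interest, followed by "pulmonary AEs, renal AEs, endocrinopathies, rash, uveitis and visual complaints, lipase/amylase elevations, and infection". Section 2.3.2.1 counts among nivolumab's important identified risks "immune-related hepatitis, immune-related nephritis and renal dysfunction, immune-related endocrinopathies". Section 8.3.6.3.1, the hematologic AESI section, records that "thrombocytopenia, anemia, and autoimmune hemolytic anemia were reported with nivolumab used in the oncology setting".

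**The concern.** Section 5.6.2 presents Table 10 as complete for its three groups, so a programmer would apply it as a closed list. An event coded to autoimmune hepatitis or haemolytic anaemia would then be left out of the hepatic or hematologic row, even though the protocol discusses it under that heading. For endocrine events there is no row and no list. Whether any of these events reaches the AESI endpoint depends on one judgement by an investigator who knows the treatment, with no prespecified list or review to set against it.

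The endocrine gap matters most. The SAP's version history reports that nivolumab dosing was halted "Based on the observation of two cases of potential hyperthyroidism", and it also records the view that the related protocol amendment did not affect the SAP.

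**Working it through.** The documents give no figure to reproduce, so the check compares lists.

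**1. Protocol AESI groups against SAP source.** Protocol 8.3.6 names 13 groups.

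| Source in SAP 5.6.2 | Groups | Number |
|---|---|---|
| Term list in Table 10 | ALT/AST and hepatic, renal, hematologic | 3 |
| Dedicated eCRF source | injection site reactions, infusion reactions | 2 |
| Immune-related question only | gastrointestinal, neurological, pulmonary, endocrine, rash, uveitis/visual, lipase/amylase, infection | 8 |

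3 + 2 + 8 = 13. Rash also has its own CRF pages and a graded listing, but no AESI term list.

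**2. Contents of Table 10.**
- ALT/AST: 12 terms, all for enzymes or liver function. Hepatitis or liver-injury terms: 0.
- Hematologic: Autoimmune aplastic anaemia, Immune-mediated cytopenia, Anaemia and Haemoglobin decreased are present. Haemolytic anaemia terms: 0.
- Renal: 93 distinct terms, including Nephritis, Nephritis allergic and Tubulointerstitial nephritis. The immune renal events are therefore covered.
- Whole table: 0 thyroid, adrenal or pituitary terms. The one diabetes term is Nephrogenic diabetes insipidus, a renal condition.

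**3. What happens to an event under these rules.**
- Reported as an ALT flare: protocol 8.3 codes it to alanine aminotransferase increased, which is listed. Caught.
- Haemolysis also reported as anaemia or a haemoglobin fall: listed. Caught.
- Coded only to a hepatitis or haemolytic anaemia term: outside the hepatic or hematologic row whatever the investigator answers, and in the AESI count only if the question is answered yes.
- Thyroid or other endocrine event: in the AESI count only if the question is answered yes.

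**4. Severity.** Section 5.6.2 lists six AE summary tables: all AEs, serious AEs, AEs leading to discontinuation, by relationship, leading to dose interruption or modification, and leading to systemic corticosteroids. None is by grade. AESI incidence is summarised by phase and overall. Grade is specified only for a rash listing. Graded laboratory tables in 5.6.3.1 do not fill this gap, because protocol Appendix 8 allows an AE's grade to differ from that of the laboratory value behind it.

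**5. Size.** Arm sizes are 18 and 19 (SAP 3). For one missed participant with no other qualifying AESI, 1/18 = 5.6 points and 1/19 = 5.3 points.

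**The case against.** The strongest reply is that little is lost from safety reporting. All treatment-emergent AEs are tabulated, with separate tables for those leading to discontinuation or systemic corticosteroids. Biochemical flares are derived from laboratory values, and an independent panel reviews ALT flares. This stands, and it confines the point to the AESI tabulation.

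Second, whether an event is immune-related is a causal judgement that a term list cannot make. An eCRF question is a legitimate prespecified method, and protocol 8.3.6.2 tells investigators to treat inflammatory events as immune-related unless another cause is clear. This also stands as a reason to keep the flag. It does not supply a cross-check, and a rule about inflammatory events does not clearly reach an asymptomatic TSH change.

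Third, autoimmune hemolytic anemia appears in the protocol as background from oncology, while the parameters monitored are platelets, hemoglobin and neutrophils. That is fair, but the event is still named in the hematologic AESI section, and the list meant to define that group leaves it out.

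Some stronger readings are tempting but not supported:
- A reader might infer that thyroid laboratory data go unanalysed, because "Change from baseline over time will be summarized for chemistry, hematology, urinalysis tests and renal biomarkers and displayed" leaves out the Other Tests group that holds TSH, T3 and T4. But Table 5 includes them, and shift and worst-abnormality tables apply to each laboratory parameter.
- Hepatitis B reactivation may look like a missing hepatic term. Its coding rule in protocol 8.3 applies off NA treatment, and a footnote says participants here stay on NA.
- Immune thrombocytopenia may look like another omission, but the protocol never names it. Thrombocytopenia itself is listed.
- The two potential hyperthyroidism cases might be taken as evidence of undercounting. They were recognised and acted on, and nothing suggests they went unflagged.

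**Conclusion.** The point holds for the AESI tabulation and for the missing severity tables, not for safety reporting as a whole. Table 10 is a closed list that would leave events coded to hepatitis or haemolytic anaemia terms out of the hepatic and hematologic groups. The immune-related group, including the endocrine events, rests on the investigator's answer alone. No AE or immune-related AE table by grade is listed, although a secondary endpoint includes severity.

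A missed event does not automatically lower the endpoint. The proportion counts participants, so it changes only if that person has no other qualifying AESI, such as an injection site reaction or an ALT rise. In that case the change is 5.6 points in Arm 1 or 5.3 in Arm 2, assuming all 18 and 19 participants are in the safety set. The documents do not show how often this would occur or in which direction open-label flagging would err. Both arms receive nivolumab and the safety analysis is descriptive, so no formal conclusion is at risk.

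**What to change.** In SAP Appendix 8:
- add autoimmune and other haemolytic anaemia terms to the hematologic list;
- add immune-mediated and autoimmune hepatitis terms to the hepatic list;
- add a MedDRA v25.0 immune-related term list that at least covers thyroid and other endocrine events.

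In SAP 5.6.2, keep the investigator flag, show list-based and flagged counts side by side, and tabulate AESIs, including immune-related AEs, by worst grade. Optionally, add TSH, T3 and T4 to the descriptive and change-from-baseline summaries in 5.6.3.1. Because SAP Amendment 2 was written after the primary analysis, the terms should come from standard groupings rather than from the events observed, and the addition should be labelled as such.

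The cost is an appendix edit and table programming on AEs that are already coded, with no new data collection. The lists will catch some non-immune events; the two-source display makes these visible.
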